6. STUDY PROCEDURES

We will access the routinely collected observational data from electronic health records at Vanderbilt University Medical Center, Lahey Hospital & Medical Center, Mayo Clinic, Weill-Cornell, and Yale New Haven Health System for this study. For the routine EHR data sources, the valid dates will be from 2010 to the most recently available data. There are no patient recruitment or retention barriers in this project as all data are observational cohort data. There are significant issues around data ascertainment bias that will be addressed in more detail in Study Design & Methods. Patient level data will not leave each institution, only aggregate data or distributed regression analyses, which will remove the requirement for a data sharing agreement and streamline the execution of the project. We will leverage each site's PCORNet common data model and the VUMC site will build the code to transform the data from the PCORNet common data model to the flat analytic file necessary for statistical work.

This project will be a multi-site retrospective cohort analysis of trans-vaginally placed synthetic midurethral slings (MUS) implanted in patients for the indication of stress urinary incontinence for mid- and long-term outcomes (1 year and greater). The key exposures will be MUS devices identified by administrative codes and identifying all patients at each of the sites through administrative and device implantation data. Surgical approaches (Retropubic MUS, Transobturator MUS, Single-Incision Sling, and Adjustable Sling) will be determined through natural language processing of operative notes. We will also identify all patients that received a surgery for SUI without mesh (autologous fascial sling or burch colposuspension). The primary outcomes of interest are long-term safety outcomes relevant to these devices and defined in Section 7. In addition, using the Mayo Clinic data, we will be able to validate the

Version 2.0 [15 July 2020]

electronic data with the manually curated data from 2010-2012. Each site will also conduct manual chart review of 50 to 100 patient cases for a critical sub-set of covariates, exposures, and outcomes that the research group deems are important, in order to validate the EHR-derived data elements, and assess potential bias among those not compared with chart review. We will leverage this data to better understand how much of the data can be electronically generated and where additional information would need to be collected in an electronic environment.

Beyond the variables collected for exposures, outcomes, and cohort inclusion/exclusion, important covariates relevant to the device exposures and outcomes, and present prior to the surgery, will also be collected. These include patient demographics, chronic pain, prior abdominal surgery, receipt of urodynamic testing (structured data will not have the results), BMI, and insurance payer. In addition, chronic clinical conditions will be aggregated using the Healthcare Cost and Utilization Project's Clinical Classification Software, which reduces all ICD-9/10 codes to 285 clinically meaningful groups⁴². The CCS has been updated to include ICD-10, which is important, as this project will span ICD-9 and 10 eras. Medication exposures will be aggregated using the PCORNet instantiation of the RxNorm controlled vocabulary and leveraging this vocabulary to the Anatomical Therapeutic Chemical (ATC) Level 4 groupings, which are clinically relevant drug classes. Some co-variates may not be ascertainable in some participating sites' PCORNet CDM instances, and this will be explored and reported. Each of the outcomes, exposures, and covariates will be analyzed for counts in each site and a summarization and report will be provided to characterize the data at each site. Stratified reporting of those receiving surgery for SUI with mesh and those without mesh will be performed.

In order to determine the surgical approach, we will supplement the CDM structured data with information from pre-operative planning and operative notes, as described in more detail in Data Collection. In order to extract the information from the text notes, we will first pursue a straightforward string matching approach to extracting the surgical approach, which will include pre-oppulating the matching algorithm with the standard names of the surgical approaches and common abbreviations, and then iteratively adding terms and variations that are found in the document set for the initial Vanderbilt training corpus. Although this is not a full NLP solution, it is likely that this will be successful primarily because use of surgical approach is not likely to be negated ('we did *not* use XX approach but did use YY approach) in the immediate peri-operative reports because they are focused on a narrative of what was done. Also, the possible space of variation in how the terms are represented is not likely to be extreme given the focused nature of the need for extraction. Lastly, deployment of this type of algorithm at each of the sites is straightforward and not as complicated to ensure that it is executed and working as a full NLP solution. We also will attempt to determine the status of hand-cut slings and tensioned slings as part of the approach and surgical plan in the operative note.

Next, if the characterization of the data is sufficient for the task, we will pursue a Cox proportional hazards model analysis, with each of the outcomes assessed from the time of the surgery as a time-to-event. We will censor the time-to-event analysis with death or loss to follow-up, defined as a time period >2 years from last applicable encounter of primary care, Obstetrics & Gynecology, or Urology. The models will be executed at each institutional separately using LASSO Cox to determine the consistently included covariates in each institution⁴⁵. We will then use the final variable list and utilize the method described by Lu and colleagues that uses a distributed analysis approach to obtain an exact model solution without sharing case level data (only intermediate and aggregate model coefficients and matrices)⁴⁶.

Because bootstrapping combined with the distributed analysis method would be computationally intensive, we will utilize 10-fold cross validation across all sites for internal validation of the risk model. We assessed overall discrimination using Harrell's concordance statistic (C-statistic)⁴⁷. To provide calibration assessments, we will also evaluate the model at fixed time points of 1 year and 2 year for each outcome using the AUC and the Estimated Calibration Index (ECI)⁴⁸. The ECI looks at the squared difference between the predicted probability and an estimated observed probability, ranging between 0

Version 2.0 [15 July 2020]

and 100, with 0 meaning perfect calibration. Additionally, we will graphically analyze calibration by investigating the smoothed observed-to-predicted probability plot⁴⁸.

Lastly, we will have access to a manually collected and curated 3,472 patient case series at Mayo Clinic from 2002 to 2012 of patients that underwent surgery for incontinence². See prior publications for more details on that existing data set². We will leverage this existing case series as a validation data set to evaluate the data capture and validity of building the data set from electronic health record sources, and determine overall data fidelity, to be reported to NEST. In more detail, since we are including patients from 2010 onward at Mayo in the EHR-based analysis, we will compare transformed variable from the EHR-based analysis with those in the manually curated registry where they are comparable to assess data quality of the EHR-based data transformation process. Each site will also conduct manual chart review of 50 to 100 patient cases for a critical sub-set of covariates, exposures, and outcomes that the research group deems are important, in order to validate the EHR-derived data elements, and assess potential bias among those not compared with chart review.

6.1 STUDY DURATION AND TIMELINE

Anticipated Start Date 2/17/2020 Requested End Date 03/15/2021

6.2 PROTOCOL DEVIATION HANDLING

There is no data safety monitor board/committee. The PI and study staff will review all data collection forms on an ongoing basis for data completeness and accuracy as well as protocol compliance. The procedures by which collected data will be verified should be provided (i.e., list procedures for verification of secondary endpoint data against original source). It is anticipated that data verification will be performed by someone other than the individual originally collecting the data, or by double-data entry. A statement reflecting the results of the ongoing data review will be incorporated into the Annual Report or the IRB Continuing Review, unless the information affects the risk/ benefit profile of the study. In the event of a protocol deviation, the event will be reviewed and reported to the IRB as soon as they occur (or no later than five days after the event is identified)

7. STUDY OUTCOMES

The primary outcomes of interest are:

- Re-operation (revision, incision, excision, removal) or mesh removal
- Chronic pain, defined as pain persisting at least three months after surgery⁴⁹
- Voiding symptoms, defined as recurrence of incontinence or new retention.

All outcomes are determined in the surveillance period after surgery. Re-operation or mesh removal is defined as a surgery for any kind of mid-urethral sling, urethral bulking agent, bladder neck pubovaginal sling (autologous or allograft), or revision for mesh exposure. Resumption of voiding symptoms was defined as subsequent urinary retention, urinary incontinence, and sling revision for urinary retention. Chronic pain is defined as a new post-operative pain score >3 of 10 on vital sign data occurring over at least 3 months or greater of duration, or diagnosis codes related to abdominal and pelvic pain.

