Study Design:	This project will be a multi-site retrospective cohort analysis of patients undergoing surgery for the indication of stress urinary incontinence for mid-term outcomes (1 year and greater) and long-term (2 years and greater) among both those with and without trans-vaginally placed synthetic mid-urethral slings (MUS).
Endpoints:	 This project seeks to provide a proof of concept for post-market medical device surveillance utilizing electronic health record data, in a use case of substantial public health safety interest to the FDA, patients, and health care providers: mid- and long-term adverse outcomes related to synthetic surgical mesh implantation for stress urinary incontinence. In pursuit of this goal, this proposal will: Assess data element availability among key covariates and exposures among patients undergoing surgery for stress urinary incontinence. If data are available, to assess rates of outcomes of re-operation for SUI, mesh erosion, re-operation for mesh revision or removal, chronic pain either as a new or worsening pain or requiring re-operation and voiding symptoms either as a new symptom or requiring re-operation, each with extended surveillance windows
	 after surgery. Provide a report of additional data elements important to conduct future device post-market surveillance in implantable devices for this indication, extrapolating to other device domains.

- 4) Lastly, if the data quality and volume are sufficient, we will develop a risk prediction model for the risk of the each of the outcomes stated above among patients receiving mesh for SUI.
- Statistical Methods: Each of the outcomes, exposures, and covariates will be summarized in aggregate for each site and a summarization and report will be provided to characterize the data at each site. Stratified reporting of those receiving surgery for SUI with synthetic mesh overall, SUI with synthetic mesh implantation by surgical approach, and SUI without mesh will be performed.

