included (49 studies, 11 RCT, 38 retrospective cohort studies)³³. The studies had a complication rate of 193% for RPMUS and a complication rate of 23.8% in TOMUS surgeries. The two approaches had similar objective cure rates, but TOMUS had a lower subjective cure rate than RPMUS. In 2017, a review was published evaluating 11 RCTs and 5 non-RCTs evaluating the long term efficacy and safety of MUS in women³⁴. There was a total of 1,200 patients across 11 RCTs with individual surgical approach populations in each trial being in the 30-299 range. Ascertainment for the RCTs were good and showed no safety or efficacy differences between approaches but were limited in size, and the non-RCTs were similarly limited in size (5206 patients across 5 studies). The most recent review, in 2019, evaluated a total of 175 RCTs with 21,598 women, and noted that most studies had high or unclear risk of bias across all Cochrane domains³⁵. A network metanalysis was done from 105 trials that reported cure and 120 trials that reported improvement of symptoms, and across the 4 common surgical approaches for MUS. The key findings from this meta-analysis was that RPMUS, TOMUS, traditional sling, and open colposuspension were more effective than other procedures for SUI, but that data on long term effectiveness and adverse events were limited, particularly around comparison between MUS and non-MUS procedures. Other relevant articles are referenced here as well, but almost all of these also cite limitations in sample size, data bias collection, and evidence limitations³⁶⁻⁴¹.

The FDA is very interested in measuring the risk of mesh use for SUI for longer outcomes >1 year within electronic health record data, which are collected for routine care and can be accessed for a variety of surveillance activities. For this reason, NESTcc was approached by the FDA to engage in a collaborative consortium to pursue these concerns, and an RFP was released to study this within an electronic health record environment in which it is hoped that longer term outcomes can be ascertained. Multiple academic medical centers, including Vanderbilt University Medical Center, Yale New Haven Health System, Weill-Cornell, Mayo Clinic, and Lahey Hospital & Medical Center, were recruited to collect and analyze patient data regarding mesh implantations for SUI for the outcomes of re-operation, mesh erosion, all-cause chronic pain, and continued voiding symptoms that occur past 1 year after the surgery.

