3. STUDY OBJECTIVES

There remains uncertainty with regards to longer term outcomes among women receiving mesh slings for stress urinary incontinence, and this project seeks to address knowledge gaps for long term outcomes among mesh implantations by leveraging electronic health record data across 5 participating health systems.

Specific Aims: This project seeks to provide a proof of concept for post-market medical device surveillance by assessing the capacity of routinely collected electronic health record data to evaluate the long-term adverse outcomes related to synthetic surgical mesh implantation for stress urinary incontinence.

In pursuit of this goal, this project will:

- 1) Assess data element availability among key covariates and exposures among patients undergoing surgery for stress urinary incontinence,
- 2) If data are available, to assess rates of outcomes of mesh erosion, re-operation for SUI, reoperation for mesh revision or removal, chronic pain either as a new or worsening pain or requiring re-operation and voiding symptoms either as a new symptom or requiring reoperation, each with extended surveillance windows after surgery.
- 3) Specifically, this project will evaluate mid-term (>1 year) and long-term (>2 years) adverse events following synthetic surgical mesh implantation (mid-urethral slings) for female SUI.
- 4) Lastly, if the data quality and volume are sufficient, we will develop a risk prediction model for the risk of the each of the outcomes stated above among patients receiving mesh for SUI.

In summary, this project seeks to better understand the safety of mesh used for stress urinary incontinence by leveraging electronic health record data. The FDA intends on incorporating these data into its growing portfolio of evidence in order to help support regulatory decision making on level of risk

for these procedures and recommendations around use of mesh for this indication. This study has the potential to increase medical knowledge regarding these devices.

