4. STUDY DESIGN

This project will be a multi-site retrospective cohort analysis of trans-vaginally placed synthetic midurethral slings (MUS) implanted in patients for the indication of stress urinary incontinence for mid- and long-term outcomes (1 year and greater). We will identify all patients at each of the sites that have received a MUS through administrative and device implantation data. The key exposures will be MUS devices identified by administrative codes. Because ascertainment of the surgical approach is critical to the evaluation of post-operative complications, and has differing rates depending on the approach, we will determine which approach was used: Retropubic MUS (RPMUS), Transobturator MUS (TOMUS), Single-Incision Sling (SIMUS), or Adjustable Sling (AMUS). In prior work at Mayo, determination of the surgical approach was present in 100% of cases in the operative notes. We will also identify all patients that received a surgery for SUI without mesh (autologous or cadaveric fascial sling or burch colposuspension or bulking agents) and evaluate the same outcomes of interest in that population separately to provide an indirect comparison group. No direct comparison of mesh and non-mesh groups will be conducted. Patients with concomitant surgeries at the time of trans-vaginal mesh implantation for SUI will be included. The primary outcomes of interest are long-term safety outcomes relevant to these devices and defined in Section 7. In addition, using the Mayo Clinic data, we will be able to validate the electronic data with the manually curated data from 2010-2012². We will leverage this data to better understand how much of the data can be electronically generated and where additional information would need to be collected in an electronic environment.

Beyond the variables collected for exposures, outcomes, and cohort inclusion/exclusion, important covariates relevant to the device exposures and outcomes, and present prior to the surgery, will also be collected.

These include:

- Patient demographics
- Chronic pain
- Prior abdominal surgery
- Receipt of urodynamic testing (structured data will not have the results)
- BMI
- Insurance payer

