Outcome	Mesh Erosion	Admin Codes: ICD-9-CM codes for mesh erosion: 996.30, 996.39, 996.59, 996.60, 996.65, 996.69, 996.70, 996.76, 996.79, 939.0, 939.2, and 939.9 ICD 10 CM: T83.498A, T85.698A, T85.79XA, T83.598A, T85.79XA, T85.9XXA, T83.89XA, T85.898A, T19.0XXA, T19.2XXA, T19.9XXA Surgical Complications: ICD 9/10 629.31/T83.711 Erosion of implanted vaginal mesh ICD 9/10 629.32/T83.721S Exposure of implanted vaginal mesh ICD 9/10 996.76/T83.9 Complication of genitourinary device, implant or graft ICD9/10-PCS V58.2/30233N1, 30233P1, 30233H1 Blood transfusion ICD9/10 998.5/ T81.49XA, T81.40XS, T81.41, T81.43, T83.5, T83.6 Postoperative infection ICD 9/10 778.2/R33.9 Urinary retention		Capture as date/time Exclude 629.3- complication of implanted vaginal mesh and other prosthetic materials, 629.31- erosion of implanted vaginal mesh, or 629.32-exposure of implanted vaginal mesh because these ICD-9 were not released until 2011? ²⁸ SME determined that topical estrogen could be prescribed for other reasons
Outcome	Urethral fistula	Admin Codes ICD 9- 599.1 ICD 10-N36.0	Yes	Capture as date/time
Covariate	Prior Abdominal Surgery Or Pelvic Radiation	Admin Codes: Personal history of irradiation-V15.3/Z92.3, Irradiation cystitis- N30.4	Yes	Yes/No
	Therapy	CPT/ICD 9/ICD 10 for prior abdominal surgery:		

Protocol 1		[15 July 2020]
	Hysterectomy: 00846, 00855, 00944, 01962,	
	01963, 01969,45126, 51597, 51925, 56308,	
	58150, 58152, 58180, 58200, 58205, 58210,	
	58240, 58260, 58262, 58263, 58265, 58267,	
	58270, 58275, 58280,	
	58285, 58290, 58291, 58292, 58293,	
	58294, 58541, 58542, 58543, 58544,	
	58548, 58550, 58552, 58553, 58554,	
	58570, 58571, 58572, 58573, 58575,	
	58951, 58953, 58954, 59135,	
	59525, 59560, 59561, 59580, 59581	
	/68.9/290.711	
	Cesarean section: 00850, 59500, 59501,	
	59520, 59521, 59540, 59541/649.81/075.82	
	Appendectomy: 44950, 44955, 44960,	
	44970, 49315, 56315/V45.79/Z90.89	
	Hernia repair: 49505, 49507, 49520,	
	49521, 49525, 49550, 49553, 49555,	
	49557, 49560, 49561, 49565, 49566,	
	49570, 49572, 49585, 49587, 49590,	
	49650, 49651, 49652, 49653, 49654,	
	49655, 49656, 49657, 49659/53.5/0WQF0ZZ,	
	0WQF3ZZ, 0WQF4ZZ	
	Cholecystectomy: 47562, 47563, 47564, 47600,	
	47605, 47610, 47612, 47620/51.0-	
	51.04/0FT40ZZ	
	51.04/01 14022	
	Colectomy: 44139, 44140, 44204, 44205, 44206,	
	44141, 44143, 44144, 44145, 44146, 44147,	
	44150, 44151, 44157, 44158, 44160,44320,	
	44322, 44799, 45110, 45111, 45112, 45113,	

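### Mesh erosion is a stated outcome in the synopsis, background and Aim 2, but Section 7 omits it and the protocol never gives it a status

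*Protocol*

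**What the plan says.** Three places treat mesh erosion as an outcome of the study. The synopsis plans to "assess rates of outcomes of re-operation for SUI, mesh erosion, re-operation for mesh revision or removal". Aim 2 in Section 3 plans, if data are available, "to assess rates of outcomes of mesh erosion, re-operation for SUI, reoperation for mesh revision or removal", followed by chronic pain and voiding symptoms. Section 1.1 says that the sites were recruited "for the outcomes of re-operation, mesh erosion, all-cause chronic pain, and continued voiding symptoms that occur past 1 year after the surgery". Aim 4 adds that, if data quality and volume suffice, "we will develop a risk prediction model for the risk of the each of the outcomes stated above among patients receiving mesh for SUI".

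Section 4 then states: "The primary outcomes of interest are long-term safety outcomes relevant to these devices and defined in Section 7". Section 6 uses the same pointer ("relevant to these devices and defined in Section 7").

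Section 7 lists three primary outcomes: "Re-operation (revision, incision, excision, removal) or mesh removal", chronic pain, and voiding symptoms. Its text on the first includes a revision carried out for mesh exposure. It mentions erosion or exposure nowhere else.

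The appendix has a Mesh Erosion row of category Outcome. The row is built on diagnosis codes, is captured as a date/time and requires no operation. It carries no primary or secondary label, and Section 7 does not refer to it.

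**The concern.** The section that the protocol names as the source of its primary outcomes does not contain an outcome that its aims promise to estimate and model. An analyst working from Section 7 and one working from Aim 2 would produce different outcome sets. Under Section 7, erosion is visible only as a reason for surgery, so an erosion managed without an operation does not appear as an erosion.

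The protocol says that the FDA intends to use the results in regulatory decisions on the level of risk. Section 1.1 lists erosion among the adverse event reports that raised scrutiny of these devices. Whether an erosion rate is a primary result, a secondary result or a descriptive count should be settled before the data are seen. The protocol leaves that open.

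**Working it through.** There is no sample size or test to reproduce. The check is a comparison of the outcome lists.

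| Outcome | Synopsis | Section 1.1 | Aim 2 (modelled under Aim 4) | Section 7 | Appendix |
|---|---|---|---|---|---|
| Mesh erosion | yes, separate | yes | yes, separate | no; only a revision for exposure | yes, by diagnosis code, no status |
| Re-operation for SUI | yes | re-operation, one item | yes | merged with next row | yes |
| Re-operation for mesh revision or removal | yes | re-operation, one item | yes | merged with previous row | yes |
| Chronic pain | yes | yes | yes | yes | yes |
| Voiding symptoms | yes | yes | yes | yes | yes |

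Count: Aim 2 has 5 outcomes and Section 7 has 3. Merging the two re-operation outcomes accounts for one of the difference (5 − 1 = 4). Dropping erosion accounts for the other (4 − 1 = 3).

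Next, take a woman with a mesh sling, an erosion diagnosis and no further operation:
- Aim 2 and the appendix Mesh Erosion row: an event, dated at the diagnosis.
- Section 7, re-operation or mesh removal: not an event, because no surgery took place.
- Section 7, chronic pain or voiding symptoms: an event only if she separately meets those definitions, and then as pain or voiding, not as erosion.

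The appendix row is not usable as it stands:
- The same cell lists codes that it labels blood transfusion, postoperative infection and urinary retention.
- The cell lists 629.31 and 629.32, labelled erosion and exposure of implanted vaginal mesh. The notes column asks, with a question mark, whether to exclude them because they were not released until 2011. The Re-Operation row uses the same two codes for its mesh exposure and erosion subtype without reservation.
- 996.69 and T85.79XA appear in the erosion list, and again in the Surgical Site Infection row as infection due to implant.

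The number of unoperated erosions cannot be derived. The nearest figure, in Section 1.1, is that 1.6% of 22,252 women having SUI surgery in a state registry had erosions that required intervention. That figure does not say that intervention means surgery, and it gives no share managed otherwise.

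**The case against.** The strongest reply is that Sections 4 and 6 say only that the primary outcomes are in Section 7, and a primary list may be a subset. The appendix labels urethral fistula, surgical site infection and organ mesh perforation as outcomes too, and none is in Section 7. Erosion is defined and dated in the appendix, and Section 9.1 summarises and models each of the outcomes without restricting itself to the primary ones. On this reading only a label and a cross-reference are missing.

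Much of that stands, and it rules out several stronger readings:
- A reader might infer that no erosion rate or model will be produced. The appendix row, Aim 4 and Section 9.1 still provide for both, subject to data availability and quality.
- A reader might infer that women with unoperated erosion count nowhere. They may be events under pain or voiding symptoms.
- A reader might object that Section 7 dates the surgery instead of the diagnosis. For a re-operation outcome that is correct, and the appendix captures the diagnosis date.
- A reader might scale up the registry's 1.6% to estimate the events lost. That would need an assumed unoperated share and a reading of intervention as surgery, and the protocol supports neither.
- A reader might take the appendix note "SME determined that topical estrogen could be prescribed for other reasons" as evidence that unoperated cases were deliberately considered. It records only that the drug has other uses.

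The reply does not remove the conflict. Fistula, site infection and organ perforation are not in Aim 2. Erosion is, and it is the only Aim 2 outcome that Section 7 drops. Section 7 is the protocol's only outcomes section and has no secondary list, so nothing says that erosion was meant to be secondary. Making the analyses conditional on data does not settle its status either.

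**Conclusion.** The inconsistency is real and should be corrected. Section 7 does not match the synopsis, the background or Aim 2 on mesh erosion. It counts erosion only when it leads to a revision, and the protocol never says whether erosion is primary. The size is one of five Aim 2 outcomes without a place in the outcomes section; no figure in events or percentage points can be given. The finding is one of definition and status, not of a biased estimate. It rests on reading Section 7 as the authority for primary outcomes, which Sections 4 and 6 state, and on the absence of any passage assigning erosion a different status.

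**What to change.** Add an entry to Section 7 for mesh erosion or exposure in women who received mesh. Count it regardless of re-operation, and date it at the first erosion-specific diagnosis code or the first operation for erosion, whichever is earlier. Make it primary, in line with the aims, or state explicitly that it is not. Either choice resolves the conflict; silence does not. Keep revision for mesh exposure as a component of re-operation, and point the new entry to the appendix row.

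Settle the code list in that row at the same time:
- Remove the transfusion, postoperative infection and urinary retention codes.
- Decide whether 629.31 and 629.32 are included, and apply the decision consistently with the Re-Operation row.
- Decide how to treat codes shared with the Surgical Site Infection row.
- Name the procedure codes that count as an operation for erosion. The Mesh Removal row itself warns that some erosions managed surgically may be coded 57295 and not 57287.

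The cost is a short entry in Section 7 plus the work of agreeing the codes. The data are retrospective and the codes come from structured fields, so no new collection is needed. The downside is one more outcome to model, with few events at the small sites.

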5. TARGET POPULATION

Inclusion criteria:

- All women aged 18 or greater undergoing transvaginal surgery for stress urinary incontinence (index surgery) with or without mesh implantation
- EHR-Based study date range 2010-2019
- Inpatient or outpatient visit

Exclusion criteria:

- No primary care, ob/gyn, or urology visits in the year prior to the surgery
- Prior pelvic organ prolapse surgery
- Prior stress urinary incontinence surgery
- Prior surgery diagnosis of a urethral diverticulum ICD-9-CM code 619.0 or any urinary-genital tract fistula (codes 599.1 and 599.2) in the 90 days prior to the index surgery.

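### The voiding outcome is defined differently in Aim 2 and in Section 7, so the pooled rate mixes return of the treated incontinence with new voiding dysfunction

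*Protocol*

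**What the plan says.** The protocol defines the voiding outcome in several places.

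- **Synopsis, Endpoints:** "voiding symptoms either as a new symptom or requiring re-operation". Section 3, Aim 2, says the same: "voiding symptoms either as a new symptom or requiring reoperation".
- **Section 7, outcome list:** "Voiding symptoms, defined as recurrence of incontinence or new retention".
- **Section 7, operational text:** "Resumption of voiding symptoms was defined as subsequent urinary retention, urinary incontinence, and sling revision for urinary retention".
- **Appendix: Data Collection, voiding symptoms row:** repeats the Section 7 wording in its notes. The row's title also names urgency, obstructive symptoms and urinary tract infection. Its code list includes stress incontinence itself (ICD-9 625.6, ICD-10 N39.3) and urge and mixed incontinence. A note records that the outcome may be difficult to tell apart from what was present before surgery, but no rule follows. The row is marked as both covariate and outcome.

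The population in Section 5 is "All women aged 18 or greater undergoing transvaginal surgery for stress urinary incontinence (index surgery) with or without mesh implantation". On the role of these outcomes, Section 4 states: "The primary outcomes of interest are long-term safety outcomes relevant to these devices and defined in Section 7". Section 9.1 would model each outcome as time to event from surgery and adds no rule for pre-existing voiding symptoms.

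**The concern.** The definitions select different women. Recurrent stress incontinence managed without surgery is not a new symptom in a woman operated on for stress incontinence, so Aim 2 leaves it out while Section 7 counts it. The mismatch also runs the other way: new urgency or obstructive symptoms qualify under Aim 2, but Section 7 names only retention and incontinence.

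If Section 7 is followed, one primary safety rate pools return of the treated condition with new voiding dysfunction. A reader could not tell how much of a high rate reflects the sling causing retention and how much reflects surgery that did not hold. A single Cox model would blend predictors of both. Sections 3 and 10.2 say the FDA intends to use the data for decisions on level of risk, so the distinction matters to the user of the result.

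**Working it through.** **Side by side**

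| Event after surgery | Aim 2 and synopsis | Section 7 |
|---|---|---|
| Recurrent incontinence, no re-operation | No (not new) | Yes |
| Recurrent incontinence, re-operated | Yes | Yes |
| Incontinence that never resolved, no re-operation | No | Unclear: no symptom-free interval is set |
| New retention | Yes | Yes |
| New urgency without leakage | Yes | Not named |

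**Size.** The protocol states no expected voiding rate, so there is no figure of its own to reproduce. The inputs are the literature ranges in Section 1.1, taking its TOT figure as transobturator.

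- One-year cure: TOMUS 62–98%, RPMUS 71–97%. Failure *f* = 100 − cure: TOMUS 2–38%, RPMUS 3–29%.
- Voiding dysfunction *v*: TOMUS 0–16%, RPMUS 3–30%.
- Midpoints: TOMUS *f* = 20%, *v* = 8%. RPMUS *f* = 16%, *v* = 16.5%.

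Assuming independence, pooled rate = 1 − (1 − *f*)(1 − *v*). The failure-only share is (pooled − *v*) / pooled.

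| Setting | Pooled rate | Pooled / *v* | Failure-only share |
|---|---|---|---|
| TOMUS midpoints | 1 − 0.80 × 0.92 = 26.4% | 3.3 | 18.4 / 26.4 = 70% |
| RPMUS midpoints | 1 − 0.84 × 0.835 = 29.9% | 1.8 | 13.4 / 29.9 = 45% |
| RPMUS, *f* = 3%, *v* = 30% | 1 − 0.97 × 0.70 = 32.1% | 1.1 | 2.1 / 32.1 = 7% |
| RPMUS, *f* = 29%, *v* = 3% | 1 − 0.71 × 0.97 = 31.1% | 10.4 | 28.1 / 31.1 = 90% |

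**Effect of the independence assumption, at midpoints.** With no overlap the pooled rates are 20 + 8 = 28% (TOMUS) and 16 + 16.5 = 32.5% (RPMUS), and the failure-only shares are 20/28 = 71% and 16/32.5 = 49%. With full overlap the pooled rates are the larger of the two inputs, 20% and 16.5%, and the shares are 12/20 = 60% and 0%.

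**Effect of Aim 2's re-operation limb.** Re-operated recurrences count under both definitions. Section 1.1 says re-operation can approach 8–9%. As an illustrative bound only, suppose all of it (8.5%) were for recurrence, with no overlap. Events counted by Section 7 but not by Aim 2 would then be (20 − 8.5)/28 = 41% for TOMUS and (16 − 8.5)/32.5 = 23% for RPMUS. Section 1.1 attributes that re-operation to adverse outcomes generally, so the true reduction is probably smaller.

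**The case against.** The strongest reply is that counting recurrence looks deliberate. Section 1.1 lists recurrence of urinary symptoms among the adverse event reports that prompted the study, Section 11 says the sponsor guided the choice of outcomes, and re-operation for SUI is itself an outcome. This stands: recurrence is a legitimate outcome here, and nothing in the documents supports removing it. It does not explain why Aim 2 leaves out recurrence that is not re-operated, or why a single rate should carry both kinds of event.

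Second, the protocol handles part of the problem. The Section 7 outcome list requires retention to be new, voiding symptoms are also collected as covariates, each site reviews 50 to 100 charts, and rates and models depend on adequate data. That supplies the material for a rule, but no rule for incontinence is written.

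Three stronger readings are tempting and not supported:

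- *Persisting incontinence always counts under Section 7.* Its wording speaks of recurrence and resumption, which suggest return after relief. The absence of a symptom-free interval leaves never-cured women ambiguous, not certainly included.
- *There are three competing definitions.* Section 1.1 does mention "continued voiding symptoms that occur past 1 year after the surgery", but as background on why the sites were recruited. Two definitions conflict.
- *The risk model would mainly predict failed surgery.* At the RPMUS midpoints failure-only events are 45% under independence and 49% with no overlap, short of a majority.

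**Conclusion.** The conflict is real and lies in current text on a primary outcome. Recurrent incontinence without re-operation is counted by Section 7 and not by Aim 2. New urgency qualifies under Aim 2 and is missing from Section 7. The appendix acknowledges the difficulty with pre-existing symptoms without resolving it.

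Failure-only events could be about 7% to 90% of the pooled RPMUS rate (about 45% at midpoints), and about 70% for TOMUS at midpoints, before allowing for re-operated recurrences. A reader might infer that failure *will* swamp the rate; the ranges support only that it *can*. Nor is any midpoint ratio an upper limit: for RPMUS the pooled rate runs from 1.1 to 10.4 times the dysfunction rate over the combinations examined, and with TOMUS dysfunction at 0% the ratio is undefined.

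These sizes rest on literature ranges for one-year cure, not coded recurrence in health records, and on independence. One-year non-cure also includes never-cured women, whose status under Section 7 is unclear. The inconsistency of definition depends on none of these figures. It should be corrected before the voiding rates are produced.

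**What to change.** Use one definition in the synopsis, Aim 2, Section 7 and the appendix. Keep recurrent incontinence as an outcome, state whether persistent incontinence belongs with it, and report it separately from:

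1. new retention, or sling revision for retention; and
2. new urgency or urge incontinence.

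Determine newness from the pre-operative voiding codes already collected as covariates, with a stated look-back chosen by the investigators. Do not present the pooled composite alone as the voiding safety rate. Model the components separately where event counts allow, and otherwise report rates only.

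The cost is protocol wording and additional tables, from codes largely listed already. The real downside is fewer events per component. It will be felt most where LASSO is run site by site, for example at Lahey, which averages 84 procedures a year in the synopsis.
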